The pilot RCT study would include 60 randomly selected hypertensive patients on hypertension treatment who may receive text message reminder and/or incentives, depending on the treatment group to which they are randomly assigned. Participants will be randomly assigned to one of three treatment groups: the control group (receives care as usual plus information on importance of establishing pill-taking routines), the message group (receives daily text messages for 3 months reinforcing information on importance of establishing pill-taking routines), or the incentive group (in addition to the same daily text messages as the message group, has a chance of winning small, intermittent rewards for taking medication in accordance with established pill-taking routine). The intervention period will last for 3 months and data monitoring will occur for an additional 6 months post-intervention totaling 9 months. Participants randomized into the incentive cohort will be eligible for a drawing only if they achieve greater than 80% medication adherence. The drawing will take place once a month for the first three months of participation with a chance to receive \$0, \$25, or \$50. Outcome measures include electronically measured medication adherence, hypertension control, adherence to established pill-taking routine, and feasibility and acceptability of intervention. We hypothesize that patients in the message and incentive groups will have higher medication adherence and hypertension control compared to the control group, and that patient in the incentive group will show greater adherence to established their pill-taking routine compared to the message and control groups.

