Behavioral Economics to improve Antihypertensive Therapy Adherence (BETA)

NCT04029883

Statistical Analysis Plan

February 21, 2023

[name] MS
Director of Clinical Analytics

Cedars-Sinai Medical Center
Smidt Heart Institute

We will determine acceptability and feasibility from participants' program experience described above and the focus groups in Phase 3. To estimate preliminary efficacy, we will perform statistical analyses comparing group-level differences in the primary and secondary outcome measures. We will use an Analysis of Covariance (ANCOVA) framework to test for group differences in each outcome at 3-month intervals, controlling for the client characteristics that are found to differentiate the groups at baseline. For analyses of dichotomous variables, such as hypertension control, we will use a non-parametric McNemar's test and an analogous multiple logistic regression to control for covariates to assess group differences. In addition to static comparisons of group means for each outcome at 3-month intervals, we will take advantage of the longitudinal nature of the data by using repeated measures and time-series techniques. Specifically, a linear mixed model with repeated observations will be fit using maximum likelihood through 'xtmixed' in the software package Stata in order to study group-level temporal dynamics in daily measures of the primary and secondary outcomes.

Specific Aim 2a: The overall impact between the pooled (*Message* group + *Incentive* group) compared to the *Control* group will be evaluated using both: 1) the comparison of group means and 2) a repeated observation regression framework that controls for observable differences between study groups and the correlation between observations of the primary and secondary outcomes for the same individual over time.

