Specific Aim 2b: The impact between the more intensive *Incentive* group compared to the lower-resource *Message* group will be evaluated using the same methods as above. Through this modeling framework we will utilize a range of variables. The independent variables in the above regression models will be used not only as control variables to improve efficiency but also to learn about the paths through which the intervention works and to identify subgroups that are likely to particularly benefit from the intervention. For example, by estimating regression models with and without measures of participants' intrinsic motivation as independent variables, we can study the mediating role of motivation on the formation of behavioral routines. The conceptual framework allows for additional mediators of behavior such as present bias, which may naturally hinder the capability of some participants to establish healthy routines. One additional method for testing this effect is to form an interaction between the present bias measure and the intervention indicator variable. With respect to the dependent variables, the primary and secondary outcomes are mean antihypertensive adherence and blood pressure control, with an exploratory focus on our quantified measure of adherence routinization. Continuous variables will be assessed for normality and transformed if needed. We will conduct analyses for the whole sample as well as separately by age and sex to better understand potential heterogeneous treatment effects. Logistic models will be estimated for binary outcome measures. We will also test whether routine adherence can be predicted based on observable characteristics; if so, in the subsequent R01 study the intervention may be targeted to those least likely to form healthy pill-taking routines on their own.

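### Age and sex heterogeneity is explored by separate subgroup analyses with no treatment interaction, so the plan never estimates the difference in effect it wants to understand

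*SAP*

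**What the plan says.** The SAP (Specific Aim 2b) sets out the age and sex analyses in one sentence: "We will conduct analyses for the whole sample as well as separately by age and sex to better understand potential heterogeneous treatment effects". It gives no age cut-point, significance level or multiplicity rule, and does not say how the separate results are to be compared. No treatment-by-age or treatment-by-sex interaction appears in the SAP or in the Aim 4B analysis in Protocol section 7.1.

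The same SAP paragraph does use an interaction for another moderator: "One additional method for testing this effect is to form an interaction between the present bias measure and the intervention indicator variable". It also says that the independent variables in the whole-sample regression models will serve "to identify subgroups that are likely to particularly benefit from the intervention".

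On design, Protocol section 4.0 states: "The pilot RCT study would include 60 randomly selected hypertensive patients" and "Participants will be randomly assigned to one of three treatment groups". The allocation ratio is not given. The SAP has two contrasts: 2a, "The overall impact between the pooled (*Message* group + *Incentive* group) compared to the *Control* group", and 2b, "The impact between the more intensive *Incentive* group compared to the lower-resource *Message* group".

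**The concern.** Heterogeneity of a treatment effect is a difference between two effects. Fitting the model in women and again in men gives two estimates, each with its own interval and p-value, but nothing that measures how far apart they are relative to their joint uncertainty. The planned method therefore does not produce the quantity the sentence says it is meant to illuminate.

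The practical risk lies in interpretation. With no comparison specified, the natural reading of paired subgroup analyses is that one is significant and the other is not. In subgroups this small that pattern is common even when the effect is the same in both. An effect by sex or age could then be reported from a pilot that contains no evidence for it. The whole-sample contrasts are not affected.

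**Working it through.** The documents state no power, effect size or significance level for Aim 4B, so there is no planned figure to reproduce. The check asks how often a uniform effect would look different across two subgroups.

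**Inputs from the documents.** 60 patients, three arms (Protocol 4.0); contrasts 2a and 2b (SAP).

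**Assumptions.** Allocation 1:1:1, so 60 / 3 = 20 per arm; two-sided 0.05; no dropout; a factor splitting every arm in half; unadjusted two-sample t-tests; effect d in SD units, identical in both halves. Each half then holds 20 versus 10 patients for 2a (pooled versus control) and 10 versus 10 for 2b.

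**Formula.** The halves are independent. If each has power p, exactly one is significant with probability 2p(1 − p). This peaks at 0.50 when p = 0.5. With no effect p = 0.05, giving 2 × 0.05 × 0.95 = 0.095. Values of p come from the noncentral t distribution.

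| d (SD) | 2a: p per half | 2a: discordant | 2b: p per half | 2b: discordant |
|---|---|---|---|---|
| 0 | 0.050 | 9.5% | 0.050 | 9.5% |
| 0.3 | 0.116 | 20.5% | 0.097 | 17.6% |
| 0.5 | 0.239 | 36.3% | 0.185 | 30.2% |
| 0.8 | 0.514 | 50.0% | 0.395 | 47.8% |
| 0.9 | 0.612 | 47.5% | 0.478 | 49.9% |
| 1.0 | 0.703 | 41.8% | 0.562 | 49.2% |
| 1.2 | 0.849 | 25.7% | 0.718 | 40.5% |

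Example, 2a at 0.8 SD: 2 × 0.514 × 0.486 = 0.500. At that effect the whole-sample 2a contrast (40 versus 20) has 82% power. So an effect this trial could detect overall is also one at which subgroup significance is close to a coin toss.

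**50% is not a bound.** With unequal powers the formula is p1(1 − p2) + p2(1 − p1). For a 70/30 split, 2a at 0.8 SD gives 0.665 × 0.675 + 0.325 × 0.335 = 0.558; 2b at 1.0 SD gives 0.721 × 0.653 + 0.347 × 0.279 = 0.568. Taking age and sex together (both evenly split, 3,000 simulated trials per setting), discordance on at least one factor occurred in 15–16% with no effect, 43–52% at 0.5 SD and 64–68% at 0.8 SD.

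**Interaction test, same simulations.** False positives were 4.8–5.8% per factor and 9–11% for either factor, whatever the size of the overall effect.

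**What an interaction test can detect.** The 80% detectable interaction (normal approximation) is (1.960 + 0.842) × √[2(1/n1 + 1/n2)], with n1 and n2 the group sizes in each half:

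- 2a: 2.802 × √[2(1/10 + 1/20)] = 2.802 × 0.548 = 1.53 SD.
- 2b: 2.802 × √[2(1/10 + 1/10)] = 2.802 × 0.632 = 1.77 SD.

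These are twice the detectable whole-sample effects, 0.77 SD (2a) and 0.89 SD (2b).

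**The case against.** The strongest reply is that the SAP never says heterogeneity will be concluded from one significant and one non-significant subgroup. Its wording is exploratory, and the separate estimates could be read sensibly from their confidence intervals. That stands: the percentages describe a misreading the plan leaves open, not a rule it adopts. It does not answer the main point, because two separate intervals still give no interval for the difference.

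The calculation also depends on assumptions the documents do not supply: the allocation ratio, significance level, effect size and subgroup split. It uses plain t-tests where the SAP plans ANCOVA ("We will use an Analysis of Covariance (ANCOVA) framework to test for group differences in each outcome at 3-month intervals") and mixed models. That is fair, and is why a range is given that includes no effect and small effects.

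A further reply is that an interaction test in 60 patients has very little power. That is correct and must be stated with the fix. It does not favour separate analyses, which carry the same imprecision without displaying it.

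Two stronger readings are tempting and not supported. A reader might infer that age and sex results will be used to target the later R01 study. The SAP's R01 sentence concerns predicting routine adherence from observable characteristics, and the phrase about subgroups that benefit refers to covariates in the whole-sample models. A reader might also infer that any observed discordance would probably be due to chance. The calculation gives the chance of discordance when the effect is uniform; the reverse probability needs a prior on true heterogeneity, which the documents do not give.

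**Conclusion.** The point holds as a minor one about an exploratory analysis. The plan for age and sex gives no estimate or test of the difference in treatment effect, although the SAP already proposes the suitable tool for present bias. The size of the risk is conditional: if results are compared by significance, false discordance on one evenly split factor runs from about 10% to 50%, against about 5% for an interaction test. It is higher with an uneven split or with both factors considered. The figures rest on 20 per arm, two-sided 0.05, no dropout and unadjusted t-tests. At this sample size neither approach can say much about heterogeneity; the interaction estimate with its interval makes that visible.

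**What to change.** In Specific Aim 2b, replace reliance on separate analyses with treatment-by-sex and treatment-by-age interaction terms in the whole-sample ANCOVA, logistic and mixed models, for both contrasts. Enter age as continuous, which removes the unstated cut-point. Report each interaction with its confidence interval and label it exploratory. Subgroup estimates may still be shown, with intervals, as descriptive only. Add a sentence that heterogeneity will not be inferred from significance in one subgroup and not in the other.

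The cost is SAP wording; no new data or patients are needed. The drawback is low power: only interactions of about 1.5 to 1.8 SD are detectable with 80% power. The SAP should therefore also say that a non-significant interaction is not evidence of a uniform effect.
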